 APPENDIX 4 INVESTIGATOR’S SIGNATURE73
 APPENDIX 5 INVESTIGATOR’S SIGNATURE AMENDMENT 174

LIST OF ABBREVIATIONS

2D	2-dimensional
3D	3-dimensional
AE	adverse event
ALP	alkaline phosphatase
ALT	alanine aminotransferase
AST	aspartate aminotransferase
BMI	body mass index
BP	blood pressure
CFR	Code of Federal Regulations
CHMP	Committee for Medicinal Products for Human Use
cGMP	Current Good Manufacturing Practices
CPET	cardiopulmonary exercise testing
CRF	case report form
DILI	drug-induced liver injury
DNA	deoxyribonucleic acid
EC	ethics committee; refers to an IRB or IEC or equivalent.
EOS	End of Study
eCRF	electronic case report form
ECG	electrocardiogram
EDC	electronic data capture
EMA	European Medicines Agency
FSH	follicle-stimulating hormone
FDA	Food and Drug Administration
GCP	Good Clinical Practice
HBV	hepatitis B virus
HCV	hepatitis C virus
HCM	hypertrophic cardiomyopathy
HIV	human immunodeficiency virus
HR	heart rate
IB	Investigator's Brochure
ICF	informed consent form
ICH	International Conference on Harmonisation
IDMC	Independent Data Monitoring Committee
IEC	Independent Ethics Committee

IMP	investigational medicinal product
IRB	Institutional Review Board
KCCQ	Kansas City Cardiomyopathy Questionnaire
LS	least-squares
LV	left ventricular
LVEF	left ventricular ejection fraction
LVFS	left ventricular fractional shortening
LVOT	left ventricular outflow tract
MAD	multiple ascending-dose
MedDRA	Medical Dictionary for Regulatory Activities
MMRM	mixed effect model with repeated measures
NASH	nonalcoholic steatohepatitis
NRS	numeric rating scale
NT-proBNP	N-terminal pro B-type natriuretic peptide
NYHA	New York Heart Association
QD	once daily
QTc	corrected QT interval
QTcF	QTc Fridericia
OSS	overall summary score
PD	pharmacodynamic(s)
PK	pharmacokinetic(s)
pVO ₂	peak oxygen uptake
RER	respiratory exchange ratio
SAD	single ascending-dose
SAE	serious adverse event
SAP	statistical analysis plan
SUSAR	suspected unexpected serious adverse reactions
TBL	total bilirubin
TTE	transthoracic echocardiography, transthoracic echocardiogram
ULN	upper limit of normal
US	United States
VCO ₂	carbon dioxide production
VE	volume expired
VO ₂	oxygen uptake
VTI	velocity time integral

1 INTRODUCTION

1.1 Background

Hypertrophic cardiomyopathy (HCM), an autosomal dominant genetic disease, is defined clinically as unexplained left ventricular (LV) hypertrophy in the absence of known causes such as pressure overload, systemic diseases, or infiltrative processes ([Gersh et al, 2011](#)). The phenotypic hallmark of HCM is myocardial hypercontractility accompanied by reduced LV compliance, reflected clinically as reduced ventricular chamber size, often supranormal ejection fraction, and diastolic dysfunction. Mutations in cardiac myosin and other sarcomere proteins in patients with HCM appear to increase net power generation by the sarcomere ([Chuan et al, 2012](#); [Sommese et al, 2013](#); [Sung et al, 2012](#)), which is consistent with the generally hypercontractile state and impaired compliance of the myocardium observed clinically in patients with HCM.

MYK-461 is a first-in-class small molecule allosteric modulator of striated muscle myosin that selectively targets cardiac myosin and reversibly inhibits its binding to actin. MYK-461's profile of myosin modulation is predicted to reduce dynamic left ventricular outflow tract (LVOT) obstruction in patients with obstructive HCM by reducing systolic hypercontractility and dynamic obstruction in the near term, and reducing ventricular hypertrophy with chronic treatment. MyoKardia is developing MYK-461 for the treatment of adults with symptomatic obstructive HCM to relieve obstruction, improve symptoms, and increase exercise capacity.

In nonclinical studies, MYK-461 was specific for striated muscle myosin and selective for the cardiac isoform (see the MYK-461 Investigator's Brochure [IB]). Its targeted mechanism of action and high degree of specificity were reflected in its pharmacology in vitro and in vivo, as well as in the toxicology and safety pharmacology. In a feline model of HCM with LVOT obstruction, treatment with MYK-461 reduced contractility and relieved obstruction in an exposure-dependent manner ([Stern et al, 2016](#)). The totality of the pharmacodynamic (PD) and tolerability data observed to date can be interpreted as direct or indirect consequences of altered cardiac contractility.

Please refer to the IB for more detailed information on MYK-461.

1.2 Clinical Studies

Three clinical studies have investigated the safety and tolerability of MYK-461 to date. A double-blind, placebo-controlled, single ascending-dose study (SAD) (MYK-461-002) was conducted in healthy men. Subjects received single doses ranging from 1 mg to 48 mg. Conduct of an open-label sequential-group SAD study in subjects with clinically stable HCM (MYK-461-001) is also complete; single doses of up to 144 mg were administered. In addition, a double-blind, placebo-controlled, multiple ascending-dose (MAD) study (MYK-461-003) is being conducted in which healthy adult subjects have received multiple doses of MYK-461 up to 25 mg once daily (QD) for up to 28 days.

1.2.1 MYK-461-002

In Study MYK-461-002, single doses from 1 mg to 48 mg were administered as an oral suspension to healthy men. All dose levels were well tolerated, with no serious adverse events (SAEs), deaths, or withdrawals from study due to adverse events (AEs) reported. The incidence of treatment-emergent AEs did not appear to increase with dose. The pharmacokinetic (PK) profile of MYK-461 displayed rapid absorption and subsequent distribution followed by a long elimination phase, with a mean elimination half-life of approximately 8 days. Single doses of ≥ 12 mg of MYK-461 were associated with detectable reductions in LV contractility from baseline as assessed by 3 independent echocardiographic measures (left ventricular ejection fraction [LVEF], LV fractional shortening (LVFS), and LVOT velocity time integral [VTI]). At the highest dose studied in healthy subjects (48 mg), mean reduction in LVEF at any timepoint was -6% relative to baseline. No changes in systolic blood pressure (BP) or heart rate (HR) were detected at any of the dose levels tested in this study.

1.2.3 MYK-461-003

In Study MYK-461-003, 4 cohorts of healthy adult subjects have been dosed, each scheduled to dose for 28 days. MYK-461 was well tolerated at multiple doses up to 25 mg QD. All AEs were mild or moderate in severity, and there were no SAEs. In cohort 3, 3 of 12 subjects who received blinded treatment (either MYK-461 12.5 mg or placebo QD) had diarrhea and/or abdominal cramps. One of these subjects was discontinued due to recurrence of diarrhea upon rechallenge, and the other 2 subjects were successfully restarted on study medication. The investigator considered these gastrointestinal AEs either mild or moderate in severity

and likely related to study medication. No gastrointestinal AEs were reported in cohort 4 (MYK-461 25 mg or placebo).

Dosing in cohort 4 was stopped on Day 25 by the investigator, because 5 of 12 subjects who received blinded treatment (either MYK-461 25 mg or placebo QD) achieved the predefined stopping criterion for dose ascension of $\geq 20\%$ reduction in LVEF. All subjects remained asymptomatic.

PD evidence of reduced contractility was apparent in the higher dose-level groups (12.5 mg QD and 25 mg QD). These data, along with the PK and PD data from all subjects in all studies to date, have been incorporated into a robust PK-PD model to help inform a safe dosing strategy for the current study that is also likely to be efficacious.

2 RATIONALE FOR THE STUDY AND FOR DOSE AND DOSING SCHEDULE

2.1 Rationale for the Study

MyoKardia has studied MYK-461 extensively across a variety of pharmacological activity and nonclinical safety evaluation platforms. In clinical studies ([Section 1.2](#)), single doses of MYK-461 up to 48 mg were well tolerated in healthy subjects (MYK-461-002), and single doses of up to 144 mg have been well tolerated (except for a vasovagal reaction with asystole and hypotension in 1 of 5 subjects at the 144 mg dose) in a study in subjects with HCM (MYK-461-001). Daily doses of 25 mg were well tolerated clinically in healthy subjects for a period of 25 days, after which time dosing was suspended by the investigator secondary to concerns regarding the degree of pharmacological activity observed (MYK-461-003). The predefined stopping criterion for dose escalation (reduction in LVEF by $\geq 20\%$) was satisfied in both the single-dose study (MYK-461-001) at 144 mg and in the 28-day multiple-dose study (MYK-461-003) at 25 mg QD.

MyoKardia has designed the current study to generate multiple-dose (steady-state) data in subjects with obstructive, symptomatic HCM using an approach that conforms to established ethical standards of safe human experimentation and the requirements of Good Clinical Practice (GCP).

2.2 Rationale for Dose and Dosing Schedule

Part A

The starting dose of MYK-461 will be 10 mg for subjects who weigh ≤ 60 kg and 15 mg for subjects who weigh > 60 kg. Each subject will receive oral MYK-461 at the starting dose QD from Day 1 through Week 4. At Week 4, an individual subject's daily dose may be decreased by 5 mg, increased by 5 to 10 mg, or remain the same based on predetermined criteria (see [Section 4](#)). The subject will subsequently receive that dose from Week 5 through Week 12. The dose selection was based on PK/PD modeling and analysis of PD and safety data from all 3 MYK-461 clinical studies (MYK-461-001, MYK-461-002, and MYK-461-003).

Part B

The starting dose of MYK-461 in Part B will be 2 mg. The dose selected for this part is intended to describe the dose and concentration response for gradient reduction and exercise tolerance at lower drug exposures than those achieved in Part A. An individual subject's daily dose may be increased to 5 mg based on predetermined criteria (see [Section 4](#)). The subject will subsequently receive that dose from Week 5 (day 29) through Week 12.

3 STUDY OBJECTIVES

3.1 Primary Objective

The primary objective of this study is:

- To characterize the effect of 12 weeks of MYK-461 treatment on reducing post-exercise peak LVOT gradient in subjects with symptomatic HCM and LVOT obstruction

3.2 Secondary Objectives

The secondary objectives of this study are:

- To assess the proportion of subjects achieving an LVOT gradient response of post-exercise peak gradient < 30 mm Hg in subjects with symptomatic HCM and LVOT obstruction
- To assess the effects of 12 weeks of MYK-461 treatment on dyspnea symptom score, peak oxygen uptake (pVO_2), and volume expired (VE)/carbon dioxide production (VCO_2) slope in subjects with symptomatic HCM and LVOT obstruction
- To evaluate the PK of MYK-461 in subjects with symptomatic HCM and LVOT obstruction
- To evaluate the PD of MYK-461 in subjects with symptomatic HCM and LVOT obstruction as assessed by a variety of echocardiographic imaging parameters in subjects with symptomatic HCM and LVOT obstruction
- To evaluate the safety and tolerability of MYK-461 in subjects with symptomatic HCM and LVOT obstruction
- To evaluate the posttreatment reversibility of the effects of MYK-461 after 4 weeks of washout in subjects with symptomatic HCM and LVOT obstruction

3.3 Exploratory Objectives

The exploratory objectives of this study are:

[figure not shown]
- To assess the proportion of subjects achieving an LVOT gradient response of post-exercise peak gradient < 10 mm Hg in subjects with symptomatic HCM and LVOT obstruction
- To assess the effects of 12 weeks of MYK-461 treatment on New York Heart Association (NYHA) functional class, N-terminal pro B-type natriuretic peptide (NT-proBNP), and the Kansas City Cardiomyopathy Questionnaire (KCCQ) Overall Summary Score (OSS) in subjects with symptomatic HCM and LVOT obstruction

- To assess the effects of MYK-461 treatment on arterial pulse wave morphology assessed using an optical biosensor in subjects with symptomatic HCM and LVOT obstruction
- To assess the effect of MYK-461 treatment on heart rate and heart rhythm as assessed using a cardiac monitoring skin patch in subjects with symptomatic HCM and LVOT obstruction

4 OVERALL STUDY DESIGN AND PLAN

This is a phase 2 open-label pilot study to evaluate the efficacy, PK, PD, safety, and tolerability of MYK-461 in subjects with symptomatic HCM and LVOT obstruction. Approximately 20 adult subjects with symptomatic HCM, a resting LVOT gradient ≥ 30 mm Hg, and post-exercise peak LVOT gradient ≥ 50 mm Hg will be enrolled. Approximately 10 subjects will participate in Part A and approximately 10 subjects will participate in Part B. The study will have a 12-week treatment phase and a 4-week washout phase (Figure 1).

Figure 1 Study Schema

CPET, cardiopulmonary exercise training; D, day; HSE, hemodynamic stress echocardiography; N, number PK, pharmacokinetic sample; RE/V, resting echocardiography/Valsalva; W, week

At Screening, subjects will undergo transthoracic echocardiography (TTE) in the supine or left lateral decubitus position. In addition to a standardized complete TTE, both resting instantaneous peak LVOT gradient (baseline) and provoked peak LVOT gradient (Valsalva maneuver) will be collected. Subjects will then undergo a standard symptom-limited exercise test (hemodynamic stress echocardiography). Subjects will be assessed systematically for

symptoms of dyspnea and/or angina. Instantaneous peak LVOT gradient will be assessed immediately post-exercise by TTE.

On Day 1, resting TTE will be performed, blood samples will be drawn for PK, and subjects will have an assessment of pVO₂, VE/VCO₂, and other variables via cardiopulmonary exercise testing (CPET). After CPET, subjects will be dosed with open-label oral MYK-461 at the investigational site and will be observed for at least 1 hour after dosing, with assessment of vital signs and ECGs at 1 hour postdose. Subjects will then be supplied with MYK-461 sufficient for QD dosing at home.

Subjects will be evaluated at the investigational site at Weeks 1, 2, 3, 4, 5, 6, 7, 8, 12, and 16. At each of these visits, resting TTE will be performed and blood samples will be drawn for PK. On study visit days, study medication will be administered at the investigational site in order to collect blood samples for PK \leq 2 hours prior to dosing. At Weeks 4, 12, and 16, hemodynamic stress echocardiography will be performed and peak LVOT gradient will be assessed. CPET will be conducted between Weeks 10 and 12 (inclusive).

Part A:

The MYK-461 starting dose will be 10 mg for subjects who weigh \leq 60 kg and 15 mg for subjects who weigh $>$ 60 kg. At the end of Week 4 (Day 28), each subject's LVEF will be evaluated, and the subject's dose may be increased, decreased, or remain unchanged based on the predetermined criteria in Table 1, in consultation between the investigator and the medical monitor. If MYK-461 plasma concentration exceeds 750 ng/mL at Week 2, no dose increase is allowed, regardless of LVEF data at Week 4; however, dose decrease per LVEF data is allowed in this circumstance. The subject will subsequently receive that dose from Week 5 through Week 12.

Table 1 Part A Week 4 Dose Adjustment Criteria

Percent Decrease From Baseline in LVEF at the End of Week 4 (Day 28)	Action for MYK-461 Dose Week 5-Week 12 ^a
< 10	increase dose by 10 mg
\geq 10 and < 15	increase dose by 5 mg
\geq 15 and < 20	no change in dose
\geq 20	decrease dose by 5 mg

LVEF, left ventricular ejection fraction

^b No dose increase allowed if plasma concentration of MYK-461 $>$ 750 ng/mL at Week 2.

Part B:

The MYK-461 starting dose will be 2 mg. At the end of Week 4 (Day 28), each subject's resting (non-provoked) peak instantaneous LVOT gradient and LVEF from the Week 4 TTE will be evaluated. The subject's dose will be increased to 5 mg or remain unchanged based on the predetermined criteria in [Table 2](#) below, in consultation between the investigator and the medical monitor. If MYK-461 plasma concentration exceeds 300 ng/mL at Week 2, no dose increase is allowed. The subject will subsequently receive that dose from Week 5 (Day 29) through Week 12.

Table 2 Part B Week 4 Dose Adjustment Criteria

Percent Decrease From Day 1 in Resting TTE Instantaneous Peak LVOT gradient at the End of Week 4 (Day 28)	Action for MYK-461 Dose Week 5-Week 12 ^a
< 50%	increase dose to 5 mg
≥ 50%	no change in dose

; LVOT, left ventricular outflow tract;

^a No dose increase allowed if plasma concentration of MYK-461 > 300 ng/mL at Week 2.

For all subjects who provide consent, blood will be drawn prior to dosing on Day 1 for assessment of HCM genotype and potentially additional deoxyribonucleic acid (DNA) sequencing.

In addition, subjects may consent separately to collection of pharmacogenetic samples that will be stored for potential future analysis of genetic biomarkers of efficacy, safety-related, PD, or PK parameters as determined by future studies using clinically meaningful endpoints, through DNA sequencing or other genetic testing.

Blood samples will be collected from all subjects prior to dosing on Day 1 and at Week 12 and stored for exploratory circulating biomarker analysis, e.g., proteomic analysis related to disease activity, metabolic pathways, efficacy measures, or safety measures.

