8.2.3 Acceptable Forms of Contraception

Highly effective methods of birth control are defined as those that result in a low failure rate (< 1% per year) when used consistently and correctly. Hormonal contraceptives are not considered highly effective contraception for this study because MYK-461 could reduce the effectiveness of hormonal contraceptives. From the time of Screening through 3 months after the last dose of study medication, subjects should practice true abstinence or use effective means of contraception as follows:

- Double-barrier method (e.g., vasectomy or male using a condom and female using a diaphragm or cervical cap)
- Barrier (e.g. male using a condom) plus non-hormonal intrauterine device (IUD) or intrauterine system (IUS)
- Female is surgically sterile or postmenopausal as defined in [Section 8.2.1](#).

For male subjects only (but not partners of female subjects), documented vasectomy is also an accepted method of birth control.

8.2.4 *Reporting and Follow-up of Pregnancies*

All pregnancies in female subjects and female partners of male subjects receiving at least 1 dose of study medication will be reported if they occur anytime from first dose to 3 months after the last dose of study medication. The investigator is responsible for informing MyoKardia of the pregnancy. The subject will be asked to provide information on the outcome of the pregnancy, including premature termination. Spontaneous miscarriage and congenital abnormalities will be reported as SAEs.

9 **STUDY ASSESSMENTS AND PROCEDURES**

The investigator is responsible for ensuring that all staff involved in the study are familiar and comply with the content of this section.

The following describes the study procedures to be performed during the study. Additional details are provided in [Appendix 1](#) of this document. When several assessments are to be conducted at the same timepoint, the preferred order of assessments is ECG, vital signs, laboratory assessments (including PK), then TTE. The order of assessments may vary slightly at specific timepoints (e.g., 1 hour postdose) to facilitate the most contemporaneous performance of the required assessments. Unscheduled or additional safety assessments may be performed if necessary in the opinion of the investigator.

For assessments that require the subjects to be in a semi-recumbent or supine position, assessments should be conducted with subjects in the same position at all timepoints.

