9.1.1.1 Resting Transthoracic Echocardiography

Resting TTE will be assessed throughout the study. Instantaneous peak LVOT gradient (baseline) and provoked peak LVOT gradient (Valsalva maneuver) will be assessed. Ejection fraction (2-dimensional [2D] and 3-dimensional [3D]), LVFS, global longitudinal strain by speckle tracking, and LVOT VTI will be analyzed, along with a variety of other echocardiographic measures (see Study Reference Manual).

Resting TTE should be performed prior to hemodynamic stress echocardiography or CPET.

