9.1.1.3 Cardiopulmonary Exercise Testing

CPET and exercise ECGs will be conducted using a treadmill at designated visits ([Appendix 1](#)). Symptom-limited exercise tests will be performed after a 4-hour fast (water is allowed). Subjects will be encouraged to perform maximally to achieve their expected HR. The following will be assessed: oxygen uptake (VO_2), VCO_2 , VE, VE/VO_2 , VE/VCO_2 , and respiratory exchange ratio (RER).

9.1.2 *Dyspnea Numeric Rating Scale*

The Dyspnea NRS is a validated measure of present dyspnea ([Gift and Narsavage, 1998](#)). Patients rate their shortness of breath by designating a number from 0 to 10, with 0 being “no shortness of breath” and 10 being “shortness of breath as bad as can be.”

9.1.3 *Kansas City Cardiomyopathy Questionnaire*

The KCCQ is a self-administered 23-item questionnaire that quantifies physical limitation, symptoms, quality of life, social interference, and self-efficacy ([Green et al, 2000](#)). The OSS is derived from the physical limitation, symptom, quality of life, and social interference domains. Scores range from 0 to 100, with higher scores reflecting better health status.

9.1.4 *New York Heart Association Class*

The NYHA functional classification of heart failure assigns patients to 1 of 4 categories based on the patient’s symptoms and objectives assessments ([Table 3](#)).

Table 3 **New York Heart Association (NYHA) Functional Classification of Heart Failure**

Class	Patient Symptoms
I	No limitation of physical activity. Ordinary physical activity does not cause undue fatigue, palpitation, dyspnea (shortness of breath).
II	Slight limitation of physical activity. Comfortable at rest. Ordinary physical activity results in fatigue, palpitation, dyspnea (shortness of breath).
III	Marked limitation of physical activity. Comfortable at rest. Less than ordinary activity causes fatigue, palpitation, or dyspnea.
IV	Unable to carry on any physical activity without discomfort. Symptoms of heart failure at rest. If any physical activity is undertaken, discomfort increases.
	Objective Assessment
A	No objective evidence of cardiovascular disease. No symptoms and no limitation in ordinary physical activity.
B	Objective evidence of minimal cardiovascular disease. Mild symptoms and slight limitation during ordinary activity. Comfortable at rest.

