9.3.1 Medical History

A complete medical history will be recorded at the Screening visit, which will include evaluation (past or present) of the following: general, head and neck, eyes, ears, nose, throat, chest/respiratory, heart/cardiovascular, gastrointestinal/liver, gynecological/urogenital, musculoskeletal/extremities, skin, neurological/psychiatric, endocrine/metabolic, hematologic/lymphatic, allergies/drug sensitivities, past surgeries, substance abuse, or any other diseases or disorders as well as participation in clinical studies (study medication and/or device or other therapy).

9.3.2 *Physical Examination*

At Screening, Day 1, Week 12, and Week 16, a complete physical examination will be conducted including a neurological examination (gross motor and deep tendon reflexes), height (Screening only) and weight, and assessment of the following: general appearance, skin, head and neck, mouth, lymph nodes, thyroid, abdomen, musculoskeletal, cardiovascular, neurological, and respiratory systems. At all other visits, an abbreviated cardiopulmonary physical examination will be conducted, with other systems assessed as directed by interval history.

Height (cm) and body weight (kg) will be measured at Screening, and BMI (kg/m^2) will be calculated. Subjects will be required to remove their shoes and wear clothing as specified by the clinical site.

9.3.3 *12-Lead ECG*

Triplicate 12-lead ECG evaluations will be performed after 10 minutes of rest at Screening and at all study visits. All ECG data will be sent to a central cardiac laboratory.

On Day 1, ECG will be performed within 2 hours predose and at 1 hour postdose. At all other visits, ECGs will be taken prior to dosing.

The investigator will judge the overall interpretation as normal or abnormal with clinical significance. Only the overall evaluation (normal/abnormal) will be recorded in the eCRF. The investigator will review the ECG and correlate abnormal findings with any other clinical findings, subject's medical history, and laboratory data to determine the clinical importance of the finding.

The investigator may add extra 12-lead ECG safety assessments if there are any abnormal findings or if the investigator considers it is required for any other safety reason. These assessments should be recorded as an unscheduled assessment.

9.3.4 *Vital Signs*

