9.3. Vital Sign Measurements

Vital signs, to be assessed at each study visit, include temperature, HR, respiratory rate, and blood pressure (BP) after resting for at least 5 minutes. Vital signs will be obtained with the subject in the same position; BP and HR should be the mean of 3 measurements taken ≥ 5 minutes apart. BP should be taken via an automated recorder.

On Day 1 of dosing, vital signs will be taken predose and at 1 hour postdose. At all other visits, vital signs will be taken prior to dosing.

Summary tables presenting observed values and changes from baseline will be presented for vital sign data, including systolic BP (mmHg), diastolic BP (mmHg), temperature ($^{\circ}\text{C}$), pulse (bpm), and respiration (breaths/minute) for subjects in the Safety set.

Changes from baseline at each scheduled post-baseline visit will be presented. All vital sign data by subject will be presented in a listing.

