9.5. Electrocardiogram

Triplicate ECG recordings will be obtained at each scheduled timepoint and the average of the three readings will be used to determine ECG intervals, including QRS, heart rate, PR, QT, Corrected QT interval using Fridericia's formula (QTcF), Corrected QT interval using Bazett's formula (QTcB) and RR. Missing ECG data will not be imputed. If one or two replicates are missing, the average will be calculated on the available replicates.

ECG Numeric Variables

HR, PR, QRS, QT, QTcF, QTcB, and RR will be summarized using descriptive statistics. The change from baseline of these ECG parameters at each timepoint will be listed for each subject. For each timepoint of measurement, the changes from baseline will be summarized using descriptive statistics.

Categorical Analysis

The cumulative incidence count and percentage of subjects with any postdose QTcF values of > 450 msec, > 480 msec, and > 500 msec will be tabulated for all subjects. Subjects will be listed with corresponding baseline values, Δ QTcF, and baseline and treatment HR. The cumulative incidence count and percentage of subjects with Δ QTcF increase of > 30 msec and > 60 msec will be tabulated. Also subjects with QTcB/QTcF >480 ms and/or change from baseline in QTcB/QTcF >60 ms will also be listed in a separate listing.

Morphology Findings

New ECG morphologies for each subject not present on any ECG at baseline for that subject will be summarized for all observation timepoints combined.

The number and percentage of subjects having new morphology changes from baseline will be reported, and summarized as QTc Prolongation, ST depression, ST elevation, T-waves biphasic, T-waves flat, T-wave inversion, or U-wave abnormality.

ECG overall interpretation by visit will be presented in a listing.

For the schedule of ECG test, please refer to Appendix 1.

10. Pharmacokinetics

Blood samples for plasma PK analysis of MYK-461 will be collected within 2 hours prior to dosing at the following timepoints: Day 1, Week 1, Week 2, Week 3, Week 4, Week 5, Week 6, Week 7, Week 8, Week12 and Week 16 or End of Study (End of Treatment + 4 Week) for Part A and Part B.

Concentrations that are BLQ will be treated as zero for descriptive statistics. All missing concentrations will be treated as missing for descriptive statistics.

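### The Day 1 one-hour post-dose change in ECG and vital signs mixes recovery from a maximal exercise test with any acute drug effect, and the SAP pools that ECG into its QTcF and morphology counts

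*Protocol*

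**What the plan says.** - **Order before dosing.** The opening of protocol section 9 states that "the preferred order of assessments is ECG, vital signs, laboratory assessments (including PK), then TTE". Section 9.1.1.1 adds "Resting TTE should be performed prior to hemodynamic stress echocardiography or CPET". The Day 1 list in section 9.5.2 has ECG, vital signs, resting TTE and CPET all before the dose.
- **Exercise.** Section 9.1.1.3 makes CPET symptom-limited: "Subjects will be encouraged to perform maximally to achieve their expected HR".
- **Dose.** Section 4: "After CPET, subjects will be dosed with open-label oral MYK-461 at the investigational site".
- **Timing of readings.** Protocol section 9.3.3: "On Day 1, ECG will be performed within 2 hours predose and at 1 hour postdose". SAP 9.3: "On Day 1 of dosing, vital signs will be taken predose and at 1 hour postdose". At every other visit both are taken before the dose (protocol 9.3.3 and 9.3.4).
- **Baseline.** SAP section 4 takes the latest available value before the first dose.
- **Use of the ECG.** SAP 9.5 summarises change from baseline at each timepoint. It counts subjects cumulatively with "any postdose QTcF values of > 450 msec" (also above 480 and 500 msec) and with QTcF increases above 30 and 60 msec. It pools new ECG morphologies over all timepoints.

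**The concern.** The pre-dose reading is at rest before maximal effort, and the post-dose reading follows that effort. Heart rate, blood pressure and repolarisation can all be shifted by recent exercise. A difference at 1 hour could be recovery, drug or both, and recovery could also hide a drug effect of opposite sign. The protocol reports rapid absorption (section 1.2.1), so this is the one scheduled point that looks for an acute effect of the first dose. The SAP then carries the 1-hour ECG into outputs that a reader will take as drug safety results, with nothing to mark it as post-exercise.

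**Working it through.** The plan states no figure to reproduce on this point. The check is of sequence, timing and destination.

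**1. Sequence.** Section 9 puts ECG and vital signs before TTE, section 9.1.1.1 puts TTE before CPET, and section 4 puts CPET before the dose. Chained together: ECG and vital signs, then TTE, CPET, dose, and the 1-hour ECG and vital signs.

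**2. Timing limits.**
- Pre-dose ECG to post-dose ECG: at most 120 + 60 = 180 minutes, with CPET in between.
- End of CPET to post-dose ECG: only about 60 minutes is guaranteed, because no gap between CPET and dose is set.

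**3. Can anything separate the two effects?** There is no randomised control (section 6.1), no day with exercise but no drug, and no ECG or vital-sign set between CPET and dose.

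**4. Share of the data.** Scheduled ECG timepoints after first dose are Day 1 at 1 hour (1), Weeks 1 to 8 (8), Week 12 (1) and Week 16 (1), which makes 11. One of the 11 is affected.

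**5. Where the 1-hour values go.**

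| Output | 1-hour value included? |
|---|---|
| ECG change from baseline by timepoint (SAP 9.5) | Yes |
| Cumulative QTcF counts above 450, 480, 500 msec (SAP 9.5) | Yes; one value classifies the subject |
| Cumulative QTcF-increase counts above 30, 60 msec (SAP 9.5) | Yes |
| New morphologies, all timepoints combined (SAP 9.5) | Yes |
| Vital-sign change summaries | Unclear: protocol 11.3.8.3 refers to timepoints after Day 1, SAP 9.3 to post-baseline visits |
| Concentration-QTc model (SAP 11) | Should not be: it needs matching concentrations, and PK samples are pre-dose only (SAP 10). Not stated |
| Dose adjustment (protocol section 4) | No: uses LVEF, resting gradient and Week 2 concentration |
| Primary endpoint | No |

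With 10 subjects in a part, one subject reclassified by the 1-hour ECG moves a percentage by 1/10 = 10 points.

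**6. Illustration, on assumed values only.** Take n = 10, no drug effect, a residual exercise shift d in heart rate and a standard deviation s of the change. The probability that a 95% t-interval excludes zero comes from the noncentral t with 9 degrees of freedom and noncentrality d√10/s. For d = 5 and s = 5 the noncentrality is 3.16.

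| Residual d (bpm) | s = 5 | s = 8 | s = 10 |
|---|---|---|---|
| 3 | 0.40 | 0.19 | 0.14 |
| 5 | 0.80 | 0.42 | 0.29 |
| 10 | 1.00 | 0.94 | 0.80 |

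Both d and s are assumptions. The table shows only that a residual of a few beats could look like a drug effect. It does not show that such a residual exists.

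**The case against.** **Later readings are on drug.** A reader might infer that all of the trial's post-dose ECG and vital-sign data are confounded. The documents do not support that. With a mean half-life of about 8 days (protocol 1.2.1) and daily dosing, the pre-dose readings at Weeks 1 to 12 are on-treatment readings and, in the preferred order, precede any exercise that day. Under a one-compartment assumption, accumulation is 1/(1 − 2^(−1/8)), about 12-fold, so the first dose is also the point of least exposure. This stands and limits the point to same-day post-dose readings.

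**The effect may be small.** ECGs follow 10 minutes of rest and are triplicate. Vital signs follow at least 5 minutes of rest, with blood pressure and heart rate averaged over three readings. QTcF corrects for rate. Single doses up to 48 mg produced no detected change in systolic pressure or heart rate in healthy men (protocol 1.2.1). A reader might nevertheless assume a residual of 5 to 10 bpm or mm Hg; no source in the documents supports that figure. The safeguards reduce carry-over by an unknown amount and do not identify its source.

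**The order is only preferred.** Section 9 allows small departures, its list does not mention CPET, and the Study Reference Manual, which is not available here, may set a recovery time. This is fair. However, if a site took the ECG after CPET but within 2 hours of the dose, the SAP rule would make a post-exercise value the baseline for every visit. That flexibility is a further reason to be explicit.

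**Vital signs may already be out of the change summaries, and the ECG change is shown by timepoint.** This is partly right. It does not deal with the cumulative QTcF and pooled morphology counts.

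**Conclusion.** The point holds in a limited form. If the preferred order is followed and no recovery period is set elsewhere, the Day 1 one-hour change from baseline cannot be read as an acute drug effect, or as evidence that there is none. It concerns one scheduled set of readings per subject in about 20 subjects, and the size and direction of any bias cannot be derived from the documents.

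It would be too strong to conclude that the trial's cardiac safety assessment as a whole is compromised. The later on-treatment readings are sound, no dose decision or primary analysis uses the 1-hour value, and individual 1-hour readings still serve to watch each subject for acute intolerance. The fault is one of interpretation and reporting. It is worth correcting because the SAP mixes this ECG into counts where its origin can no longer be seen.

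**What to change.** **SAP wording (recommended).**
- In 9.3 and 9.5, show the Day 1 one-hour values in their own row, labelled post-exercise.
- In 9.5, give the cumulative QTcF, QTcF-increase and new-morphology counts with and without the 1-hour ECG.
- Keep every value in the listings, so that nothing the protocol asks for is dropped.
- In section 11, state that the 1-hour ECG is outside the concentration-QTc model because it has no matching PK sample.

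The cost is text and a few extra table rows.

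**Optional addition.** Take one resting ECG and vital-sign set after CPET recovery and before the dose, as the reference for the 1-hour change only. Vital signs alone need 5 minutes of rest plus two 5-minute gaps between three readings, which is 15 minutes; with the ECG, allow about 15 to 25 minutes per subject. This needs a protocol change. SAP sections 4 and 11 must also name the pre-CPET set as study baseline, or the rule that takes the last value before dosing would select the new set. It helps only in part, because recovery may continue after the added reading.
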